# Welfare of the Researcher

The supervisory team will be aware of the time and location of all focus groups and the researcher will follow the university's lone working policy for interviews being conducted in participant's homes. The researcher will provide the supervisory team with a sealed envelope containing the participants name and the address where the interview is taking place. The researcher will carry a mobile phone at all times to ensure they are contactable and their contact details will be provided to all members of the supervisory team. The team will be informed of the researcher's method of transport and approximate time the interview/focus group will be completed. The researcher will contact the team via text on arrival and will call to confirm when the interview has been completed. If the team does not receive a phone call within an hour of the estimated completion time and are unable to contact the researcher, they will open the sealed envelope and contact the authorities with the information. The emotional wellbeing of the researcher will also be considered, due to the emotional impact of working with a patient group with an end-stage illness, and debriefing will be provided by the supervisory team if needed (Social Research Association, 2001)

# **Dissemination of Results**

The protocol for the study, findings from the systematic review, feasibility randomised controlled trial, process evaluation and economic evaluation will be submitted for publication

in high quality peer reviewed journals and presented at national and international conferences including the British Renal Symposium and the EDTNA/ERCA annual conference. Service users will also be involved in the dissemination of findings, and researchers will collaborate with the Northern Ireland Kidney Patient Association and Kidney Care UK. The economic evaluation data collection form will be listed on the MRC's Database of Instruments for Resource Use Measurement (DIRUM). A social media plan will be created to incorporate platforms such as Twitter and Facebook to disseminate information, progress, events and findings from the study.

### **Appendix 7:** Distress Protocol Patients

# **Distress Protocol - Patients**

### **Rationale**

Patients with end-stage kidney disease receiving haemodialysis are potentially vulnerable and experience lower health related quality of life compared to the general population, and are at a higher risk of developing mental health issues such as anxiety and depression. Discussions surrounding these issues may cause distress. Therefore it is important that researchers are sensitive to the person's distress and acts to minimise any potential exacerbation, and help identify agencies or services that can provide support.

### Distress Protocol for Phase 2 and 3

Distress

- A participant indicates that they're experiencing high levels of emotional distress
- A participant exhibits behaviour that suggests the questionnaire or interview is causing distress, such as crying, shaking, trembling, difficulty speaking

Stage 1 response

- Stop the discussion
- •Offer immediate support
- •Assess mental status. The researcher is a registered mental health nurse and will conduct a brief mental state examination, exploring the thoughts and feelings the person is experiencing in that moment.

Review

- •The research will ask the participant if they feel able to carry on.
- •The research will recommenced completing the questionnaire or interview if they feel able.
- If the participant feels unable to continue the researcher will move on to stage 2.

Stage 2 response

- Discontinue data collection/interview
- •Offer the participant, with consent, for the researcher to approach a member of the clinical team for further advice or support.
- Encourage the participant to contact their GP or mental health provider
- Provide the participant with information relating to health psychology services and NIKPA

- Follow up participant during next visit to the unit, with the patient's consent.
- •Encourage the participant to contact the researcher if they continue to experience increased distress.

### **Appendix 8:** Distress Protocol Healthcare staff

## Distress Protocol - Healthcare Staff

### **Rationale**

Patients with end-stage kidney disease experience difficult symptoms and have high rates of mortality. It is likely that during the course of this study healthcare staff working on the haemodialysis unit will experience the deterioration of the health of their patients, and potentially the death of patients. Discussions surrounding these issues may cause distress. Therefore it is important that researchers are sensitive to the person's distress and acts to minimise any potential exacerbation, and help identify agencies or services that can provide support.

### **Distress Protocol for Phase 3**

### Distress

- •A participant indicates that they're experiencing high levels of emotional distress
- A participant exhibits behaviour that suggests the questionnaire or interview is causing distress, such as crying, shaking, trembling or difficulty speaking

# Stage 1 response

- Stop focus group and offer immediate support
- •Assess mental status. The researcher is a registered mental health nurse and will conduct a brief mental state examination, exploring the thoughts and feelings the person is experiencing in that moment.

### Review

- •The researcher will ask the participant if they feel able to carry on.
- •The researcher will recommence the focus group if they feel able.
- •If the participant feels unable to continue the researcher will move on to stage 2.

# Stage 2 response

- •Discontinue interview and the researcher will accompany the participant to a private area.
- •Encourage the participant to contact their GP or mental health provider.
- Encourage the participant to speak to a member of their clinical team, eg. manager
- Provide the participant with information relating to supportive services or occupational health

- Follow up participant during next visit to the unit, with the participant's consent.
- •Encourage the participant to contact the researcher if they continue to experience increased distress.

### **Appendix 9**: Distress protocol – Suicide risk

## Distress Protocol - Suicide Risk

### Rationale

Patients with end-stage kidney disease are at high risk for developing mental health issues such as depression. One consequence could be an increased risk of suicide. The researcher will be administering the Hospital Anxiety and Depression scale during the project, and while this scale is not diagnostic of mental health issues and does not ask information on suicide or thoughts of life not worth living, the questionnaire may prompt patients to spontaneously disclose thoughts of suicide. Therefore it is important that researchers respond appropriately to reduce risk of harm.

### **Distress Protocol for suicide risk**

# Suicidal ideation

•A participant indicates that they're experiencing thoughts of life not worth living or active suicidal ideation.

# Stage 1 response

- Stop the discussion
- •Offer immediate support
- •Assess immediate risk. The researcher is a registered mental health nurse and ASIST trained, and will conduct a brief risk assessment, identify protective factors, the presence or absence of an active plan and the ability to complete a suicide plan. This assessment will not consistute a formal mental health assessment as the researcher is not present within a clinical capacity so onward referral will be necessary.

# Stage 2 response

- •If the participant is assessed not to be at immediate risk the researcher will inform the nurse in charge of the identified issues and the healthcare professional can determine the best course of action, including potential onward referral to the renal counsellor, GP or RAID.
- If the participant is assessed as being at immediate risk, confidentiality will be breached and the nurse in charge will be informed.
- •The nurse in charge will be advised to contact the Rapid Assessment Interface and Discharge team, who can provide an emergency assessment and onward referral to a crisis response team.

- Follow up participant during next visit to the unit, with the patient's consent.
- Conduct another risk assessment and review current mental state.
- •As participants are not being excluded as a consequence of mental health issues, they will be asked if they wish to continue in the study. If the participant wishes to continue in the study risk will be reviewed at each follow-up session.

The input from healthcare professionals to the distress protocol is an important consideration. Even though the potential for a spontaneous disclosure of suicide or harm is low, a risk assessment will be taken by the researcher who is a trained Mental Health nurse. The reason for the referral through the direct care team is procedural and reflects the standard process within the HSC. The researcher as an experienced mental healthcare professional will be able to advise the care team but feels it would be inappropriate to operate outside of the standard practices on site. The Sponsor has also requested that the researcher clearly separates their research and clinical roles.

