# **Data Collection and Management**

Approximately 13 patients will be recruited into the process evaluation. Simulations have shown that this sample size of 10 should identify 80% of problems within a complex intervention (O'Cathain et al., 2014), while data saturation is likely to be reached at 12 interviews on average (Guest et al., 2006). The principle of 10 + 3 for data saturation outlines that a minimum of 10 interviews should be conducted, followed by at least 3 consecutive interviews that present no new findings (Francis et al., 2010), therefore a sample of 13 patients will be recruited for semi-structured interviews. Approximately 5 healthcare staff will be recruited into each focus group, with a proposed total of 3 focus groups (Schneider et al., 2009). The dialysis unit in which the study is taking place is relatively small, therefore the focus groups will be limited by the amount of staff available who meet the eligibility criteria and the requirement to produce a manageable amount of data for the time limitations of the study (Carlsen and Glenton, 2011; O'Cathain et al., 2014). However, these are approximate sample sizes, and data collection will continue until data saturation is reached. The researcher will provide the participants with a consent form prior to commencement of the focus group (Appendix 6). Data saturation will be determined when there is no new data being found from which additional themes can be developed (Guest et al., 2006).

Data collection for the process evaluation will occur in parallel to the feasibility randomised controlled trial, during implementation of the intervention and follow up (Moore *et al.*, 2014). The semi-structured interviews will be conducted with patients in their own home to maintain

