confidentiality and avoid the power dynamic present in a clinical setting (Green and Thorogood, 2004). This approach will be flexible and patients can request that interviews occur during the haemodialysis session or on the unit if this is their preferred location. The focus groups with staff will take place in a private room on the haemodialysis unit. The process evaluation will follow the MRC guidance on process evaluations for complex evaluations (Moore *et al.*, 2014). It will therefore focus on the acceptability of the intervention, barriers and facilitators to implementation, the appropriateness of outcome measures, motivations for participation, reasons for continued engagement and potential mechanism of impact of the intervention.

The semi-structured interviews and focus groups will use interview guides consisting of open questions informed by the RE-AIM QuEST framework (Forman *et al.*, 2017). The interview guide will be flexible to ensure that participants can express and explore perspectives that they consider relevant to implementation, and will be reviewed by the advisory group and supervisory team who are responsible for providing objective oversight.

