# Welfare of Participants

The research involves participants who have an advanced illness. During the feasibility randomised controlled trial participants will be receiving an arts-based intervention whilst also receiving haemodialysis. Due to the importance of maintaining vascular access and not inhibiting the work of healthcare professionals, the intervention will be designed with input from healthcare professionals working in this clinical setting, as well as artists from Arts Care Northern Ireland who have experience adapting arts-based interventions to the clinical environment. The process evaluation will also occur in parallel to the implementation of the intervention, ensuring that any issues with the intervention are identified and can be addressed during the trial (Moore *et al.*, 2014).

As the questionnaires participants fill out explore subjects such as quality of life and mental health, and the interviews and focus groups may broach sensitive subjects relating to the experiences of living with ESKD or the experiences of working with patients who have an end-stage illness, there is a potential for participants to experience emotional distress. A distress protocol (Appendix 7, Appendix 8) will be in place to address these issues (Haigh and Witham, 2015) and participants will be provided with information regarding relevant supportive services available. Participants will be reminded they can stop the interview at any time, they are not obligated to answer questions they feel are too sensitive, or provide information they are not comfortable sharing. A renal counsellor will also be present on the advisory group and will provide guidance on maintaining the emotional wellbeing of participants. Two additional distress protocols have also been developed for the potential that a participant discloses suicidal thoughts (Appendix 9) or achieves a score on the Hospital Anxiety and Depression Scale that suggests the presence of a clinical mental health condition (Appendix 10).

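### Appendix 9's visible immediate-risk step runs only through the nurse in charge, which does not fit Phase 3 interviews held by default in the patient's home

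*Protocol*

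**What the plan says.** Appendix 9 of the Protocol (distress protocol for suicide risk) starts when a participant indicates that they are "experiencing thoughts of life not worth living or active suicidal ideation". In Stage 1 the researcher, a mental health nurse with ASIST training, stops the discussion, offers support and makes a brief risk assessment. This does not count as a formal assessment, "as the researcher is not present within a clinical capacity so onward referral will be necessary".

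Stage 2 gives the rule for immediate risk: "If the participant is assessed as being at immediate risk, confidentiality will be breached and the nurse in charge will be informed". It continues: "The nurse in charge will be advised to contact the Rapid Assessment Interface and Discharge team", which can assess urgently and refer on to a crisis team. The closing paragraph explains that referral goes through the direct care team because that is the usual health-service procedure. It says that the researcher "feels it would be inappropriate to operate outside of the standard practices on site", and that the sponsor wants research and clinical roles kept apart.

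The Phase 3 section on data collection sets the place of the patient interviews: "The semi-structured interviews will be conducted with patients in their own home to maintain" confidentiality and to avoid the power imbalance of a clinic. As the alternative, "patients can request that interviews occur during the haemodialysis session or on the unit if this is their preferred location". About 13 patient interviews are planned.

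Two other sections bear on the point. Welfare of Participants notes that "the interviews and focus groups may broach sensitive subjects relating to the experiences of living with ESKD" and introduces Appendix 9 in the same paragraph. Confidentiality and Anonymity says that evidence of serious concern for someone's safety, arising in an interview or focus group, must be passed to a third party. It does not say to whom or how.

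**The concern.** The immediate-risk step depends on a person who is on the unit, while the protocol's default place for patient interviews is somewhere else. On the unit, the nurse in charge can come to the participant, judge the situation and summon help within minutes. In a patient's home, the researcher would have to reach that nurse remotely, and the nurse would then have to reach the rapid assessment team. Meanwhile the only professional in the room has no written instruction to call for help directly.

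The stake is participant safety in a rare event with a potentially irreversible outcome. Recruitment, retention, the outcome data and the progression decision are not touched.

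**Working it through.** No arithmetic decides this point, so the check sets the relevant texts side by side.

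1. **Where the interviews happen.** Home is the default and the unit is used on request (Phase 3, Data Collection and Management). The planned number follows the protocol's own rule, 10 + 3 = 13. It is approximate, because interviewing continues until saturation. If *k* patients choose the unit, about 13 − *k* interviews are at home. The protocol gives no value for *k*. Staff focus groups are held on the unit and are unaffected.

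2. **Whether Appendix 9 reaches a home interview.** Its trigger has no limit by phase or place, and Welfare of Participants introduces it alongside the risk of distress in interviews. Its rationale, however, is written around the HADS questionnaire. Both readings can be followed through:
   - *Appendix 9 covers interviews.* The nurse-in-charge route then applies in the home.
   - *Appendix 9 covers questionnaire sessions only.* Home interviews then fall back on Appendix 7, which is expressly for Phases 2 and 3. Its visible steps offer support, the clinical team, the GP and information on services. They contain no emergency step.

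   On either reading, the visible text has no direct emergency route for a patient at home.

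3. **Who acts, by setting.** Appendix 9 does not name the nurse's unit. That it is the haemodialysis unit is inferred from the references to the direct care team, to on-site practice and to follow-up at the next unit visit.

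| Step | Interview on the unit | Interview at home |
|---|---|---|
| Assess risk | Researcher, in person | Researcher, in person |
| Inform nurse in charge | Nurse is nearby and can attend | Nurse is elsewhere and must be reached remotely |
| Contact rapid assessment team | Nurse, on the researcher's advice | Nurse, remotely, on the researcher's advice |
| Direct emergency call by researcher | Not mentioned | Not mentioned |

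4. **Whether other visible text fills the gap.** The third-party provision under Confidentiality and Anonymity allows disclosure but sets no recipient, order or method. The home-visit procedures under Welfare of the Researcher protect the researcher and are not a route for a participant at risk.

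5. **Frequency.** Appendix 9 calls the potential for spontaneous disclosure low and gives no rate. No event probability can be derived, and none is claimed.

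**The case against.** The strongest reply is that this argues from absence. The text immediately after Appendix 9 was not available for this review, and it may hold crisis contacts or further steps. The information sheet for the interviews and the university's lone-working policy were not available either. This stands as a limit: the point concerns the visible step and cannot show that no home procedure exists. It does not remove the point, because the step that can be read states a rule, and that rule is written for the unit.

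The second reply concerns scope. The rationale of Appendix 9 rests on the HADS, and SAP Table 1 schedules the HADS separately from the qualitative interview. Use of Appendix 9 at a home interview is therefore an inference from its open trigger. The inference is reasonable, and the narrower reading leaves less provision for the home.

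Third, a reader might infer that the researcher is forbidden to call emergency services, or must wait for the nurse. The documents do not say so. Stage 2 says that the nurse is told, not that only the nurse is told or that the nurse is told first. The third-party provision does not exclude emergency services, and the reluctance to work outside local practice refers to on-site practice, which does not describe a home. The nurse can be telephoned, and the researcher carries a mobile phone and has relevant training. All of this stands and makes the point smaller. What remains is that the role-separation request leaves it unstated whether the researcher may act directly.

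A reader might also think that a prolonged stay would collide with the overdue-call rule under Welfare of the Researcher. That rule acts only if no call arrives and the researcher cannot be reached. Its effect would be to alert the authorities, so it describes no harm here.

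**Conclusion.** The point holds as a minor matter of participant safety. The visible immediate-risk step in Appendix 9 is fitted to the unit and is not adapted to the default setting of Phase 3 patient interviews. Followed literally, it places two remote contacts before emergency help that the researcher could call directly.

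The size is small: about 13 planned interviews, less those held on the unit, and a disclosure potential that the protocol calls low. Trial validity is not affected. The potential gravity of a single event and the low cost of the change are what justify raising it.

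The conclusion rests on three assumptions: that the nurse in charge is the unit's nurse, that Appendix 9 applies to interviews (or that nothing more specific does), and that the unseen text does not already give a home route. If the sponsor can point to such a route, a cross-reference in Appendix 9 is enough. The documents do not support the stronger conclusions that participants interviewed at home have no protection or that the researcher is barred from acting.

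**What to change.** Add one branch to the immediate-risk step of Appendix 9 for interviews held away from the unit:

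- the researcher stays with the participant for as long as it is safe to do so;
- the researcher directly contacts emergency services, or a crisis contact agreed in advance with the sponsor and the unit;
- the researcher then telephones the nurse in charge and the supervisory team.

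State in the same place that this is an agreed exception to the on-site referral route and to the separation of research and clinical roles, limited to immediate risk away from the unit. The existing step can stay unchanged for disclosures on the unit.

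The cost is a few sentences, one contact agreed beforehand, and the agreement of sponsor and unit to that exception. The small downside is that a referral may occasionally bypass the unit's usual channel. The branch should be in place before the first home interview.

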### **Appendix 10**: Distress Protocol - HADS

### Distress Protocol – HADS

### **Rationale**

Patients with end-stage kidney disease are at high risk for developing mental health issues such as depression and anxiety. The researcher will be administering the Hospital Anxiety and Depression scale during the project, and while this scale is not diagnostic of mental health issues it can be used as a screening tool to identify high risk of depression and anxiety. Therefore it is important that the researcher identifies patients who at an increased risk so they can be properly assessed.

